This study manipulates e-cigarette nicotine flux systematically, testing the hypothesis that abuse liability will be related directly to flux among a sample of cigarette smokers. No previous study has manipulated nicotine flux and examined within-group effects, so we could not estimate effect size. Thus, we calculated a sample size to achieve a power of >0.80 with $\alpha <0.05$ and assuming a small effect size (Cohen's $f=0.20$) and moderate repeated measures correlation ($r=0.5$) in a repeated measures ANOVA with nicotine flux as within-subjects factors (N=32; GPower). In Study 2, 40 cigarette users will attend the lab for 5 sessions - no flux, low flux, cigarette-like flux, high flux, and an own brand cigarette control (always session 5). We hypothesize that flux will be positively associated with willingness to pay/work (drug purchase task, progressive ratio task) and willingness to substitute e-cigarettes for own brand cigarettes (cross-product drug purchase task, cross-product progressive ratio task), and inversely to price sensitivity (drug purchase task) for all smokers.

It is possible that we would consent up to 100 participants in order to obtain 40 participants who complete the entire study.

4. * List the study inclusion criteria:

All participants must be healthy (determined by self-report), between the ages of 18-55 (verified by photo ID), willing to provide informed consent, and attend the lab and abstain from tobacco/nicotine as required. Participants must agree to use designated products according to the study protocol.

Participants must use at least 5 cigarettes per day if they are not classified as dual users of inhaled tobacco products.

Participants classified as dual users of inhaled tobacco products must meet at least of two definitions described below:

- at least some day use of cigarettes (≥ 3 days per week at any cigarettes per day frequency) AND
- daily use of another inhaled tobacco product (e.g., e-cigarettes, cigars, pipe)

OR

- daily use of cigarettes (at any cigarettes per day frequency) AND
- at least some day use of another inhaled tobacco product (e.g., e-cigarettes, cigars, pipe; ≥ 3 days per week at any frequency).

Participants must have a 'positive' cotinine cassette result to verify nicotine use.

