The Cross Product-Progressive Ratio Task (CP-PRT). The CP-PRT asks the participants to perform work, in the form of key presses for puffs of a condition-specific product or own brand cigarette. Using a concurrent schedule (Audrain-McGovern et al., 2015, 2014; Perkins et al., 1994; Perkins et al., 2002), participants are told that they can switch from working for one product or the other as often as they wish. Participants are instructed to press either a "A" key (condition-specific ECIG) or "L" key (own brand cigarette). Consistent with relative reinforcement paradigms, the reinforcement schedule for the session-specific product remains constant at a fixed ratio FR-25 (25 presses achieved to earn a point) while the reinforcement schedule for the own brand cigarettes increases by 25 space bar presses over 10 trials, such that 25, 50, 75, 100, 125, 150, 175, 200, 225, and 250 presses are required to earn a puff (similar to Audrain-McGovern et al., 2015, 2014; Bickel et al., 2000; Epstein et al., 2007). Participants will be randomized to either receive the earned cigarette or ECIG puffs first. Cross-PRT outcome measures are 1) Breakpoint or the highest trial (out of 10 trials) that was completed for own brand cigarette puffs. Data is collected via a software program created using Python. The data file is stored locally, under a username and password protected profile. It is then copied to secure storage locations (such as Ironkey or R-Drive) after each session.

The Drug Purchase Task (DPT) assesses hypothetical tobacco product purchasing behaviors for the session specific ECIG (assessed at sessions 1-4) and own brand CIG (assessed during the own brand session). The outcomes from the DPT include the breakpoint (highest price participants were willing to pay), elasticity (change in amount purchased as price increases), Omax (highest amount individuals paid in any choice, i.e., maximum value of price*quantity), Pmax (the price associated with Omax), and intensity (amount "purchased" when the price is zero/free). Data is collected via REDCap survey and stored under username/password with specific access per user.

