Data analysis. Subjective, physiological, DPT, CP-DPT, PRT, and CP-PRT data will be prepared as reported elsewhere ([name] et al., 2017; Rusted et al., 1998; [name] et al., 2010). Elasticity is estimated using an exponential demand function with nonsystematic DTP data excluded based on two criteria: trend, or whether the participant had a general decrease in consumption from the lowest to highest price; and bounce, or whether a participant reported higher consumption at sequential higher prices (Stein et al., 2015). In general, analysis will involve a mixed (between- and within-subject) ANOVA. Demographic data will be examined to determine if there are significant between-group differences on measures that may be related to study outcomes. Unexpected between group differences will be considered as potential covariates in the primary analysis (see Evans et al., 2006). Statistical analyses may utilize regression, ANOVA, or mixed linear models. Adjustments for sphericity violations and post-hoc testing using Tukey's HSD or planned contrasts with Bonferroni corrections will be used (Keppel, 1991). Based upon the type and amount of missing data, we may use accepted techniques such as multiple imputation (Allison, 2001).

7. * The IRB only reviews research activities, so indicate for each of the study activities described in the question above or in the protocol which activities are:

- Being performed exclusively for research purposes (i.e. they would not otherwise be done apart from this study) **VERSUS.**
- Alterations of routine activities/procedures (e.g. the study is altering the timing, frequency, method, location, amount, etc.) **VERSUS.**
- Being done for other purposes and whose data/results will be used secondarily in the study (e.g. standard medical or psychological tests, routine education practices, quality improvement initiatives, etc.).

See the help text for additional guidance

All of the procedures described above are performed exclusively for research purposes. There are no alterations of routine procedure and no procedures would be performed if these individuals were not taking part in this research study.

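### The default between- and within-subject ANOVA and its between-group covariate step do not match this one-group within-subject study, and session order is in no stated model

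*Combined protocol and SAP*

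**What the plan says.** The Data analysis paragraph under Study Procedures, item 6, sets the default: "In general, analysis will involve a mixed (between- and within-subject) ANOVA". It then plans a check of demographic differences between groups, and "Unexpected between group differences will be considered as potential covariates in the primary analysis". It leaves the model open: "Statistical analyses may utilize regression, ANOVA, or mixed linear models". It does commit to "Adjustments for sphericity violations and post-hoc testing". It names no group and no session, period or sequence term.

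The design is described elsewhere. The Overview in the same item has 40 cigarette users completing five within-subject conditions. The four ECIG conditions are Latin-square ordered over sessions 1-4, and own brand comes last for everyone. The sample size justification (Study Population, item 3) rests on a "repeated measures ANOVA with nicotine flux as within-subjects factors (N=32; GPower") and lists the sessions as "no flux, low flux, cigarette-like flux, high flux, and an own brand cigarette control (always session 5").

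Three features could define a between-subject factor, but none is declared as one for analysis:
- smoker type, from the inclusion criteria: "Participants must use at least 5 cigarettes per day if they are not classified as dual users of inhaled tobacco products";
- Latin-square sequence, from the Overview;
- puff order in the cross-product progressive ratio task (CP-PRT): "Participants will be randomized to either receive the earned cigarette or ECIG puffs first".

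The only explicit two-group version of this study is in the grant text (Aim 2): 60 exclusive ECIG users and 60 dual users.

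**The concern.** With one group, a between-subject factor has no degrees of freedom, and the between-group covariate step has nothing to act on. If a group is meant, the reader cannot tell which of three candidates it is, and the choice can be made after the data are seen. The same holds for the model, since three families are allowed and the terms of none are listed.

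Order is a second gap. The plan balances the ECIG conditions over sessions by Latin square, but no stated model uses session. Own brand occupies session 5 for every participant, and the hypothesis items (Background, item 2; Study Procedures, item 1) say it will be compared with the ECIG conditions. Any change over sessions, such as practice, fatigue or familiarity with the tasks, would then be counted as a product difference.

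**Working it through.** **1. The plan's own sample size.** Inputs from Study Population, item 3: f = 0.20, r = 0.5, alpha 0.05, power above 0.80. For one group and m within-subject levels under sphericity, noncentrality = N·m·f²/(1−r), with df m−1 and (N−1)(m−1).

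| Levels | Smallest N | Power at that N | Power at 32 | Power at 40 |
|---|---|---|---|---|
| 5 | 32 | 0.814 | 0.814 | 0.902 |
| 4 | 36 | 0.808 | 0.753 | 0.852 |

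Two or three levels would need 52 or 42. So N=32 reproduces only with five levels, that is, with own brand counted, in a purely within-subject one-group model. The text does not state the number of levels; this is inferred from the match.

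**2. Flux contrasts with equally filled sequences.** Let d be an assumed linear drift over sessions 1-4, in SD, so the session shifts are 0, d/3, 2d/3 and d. Each condition falls equally often in each session, so each gains d/2 and the differences between conditions are unbiased. Without a session term, the session variation goes into error. Its sum of squares is 40 × (5/9)d² = 22.2d², which adds 22.2d²/117 = 0.19d² to an error variance of 1 − r = 0.5. That is +2.4% at d = 0.25 and +9.5% at d = 0.5.

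Simulated power (N=40, four levels, 10 per sequence; GG = Greenhouse-Geisser):

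| d | No session term | With term | No term, GG | With term, GG |
|---|---|---|---|---|
| 0.25 | 0.844 | 0.852 | 0.831 | 0.841 |
| 0.5 | 0.819 | 0.852 | 0.805 | 0.841 |
| 1.0 | 0.703 | 0.851 | 0.682 | 0.841 |

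Like for like, the gain is about 0.01 at d = 0.25 and 0.03 to 0.04 at d = 0.5. Error df fall from 39 × 3 = 117 to 114.

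**3. Flux contrasts with unequal sequences.** Recruitment and Enrollment replaces non-completers but does not say whether the replacement takes over the same sequence. At assumed completer counts of 13/11/8/8, omitting session biases the worst pair of conditions by 0.05d to 0.15d in a Williams square and 0.10d to 0.13d in a cyclic one, depending on which sequences are over-filled. The plan does not name the square.

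**4. Own brand against ECIG.** With 40 participant columns, 4 condition columns and 4 categorical session columns, the design matrix has 48 columns and rank 47. Own brand and session 5 are the same column, so the contrast cannot be estimated. With one linear session term it has 45 columns and rank 45, so the contrast is estimable, but only under an assumed trend shape.

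The bias without adjustment is the session-5 shift minus the mean shift of sessions 1-4. Linear adjustment subtracts 2.5 times the slope fitted to sessions 1-4.

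| Assumed drift | Unadjusted | After linear adjustment |
|---|---|---|
| Linear, continues to session 5 | 4d/3 − d/2 = 0.83d | 0.83d − 2.5(d/3) = 0 |
| Linear, levels off after session 4 | d − d/2 = 0.50d | 0.50d − 0.83d = −0.33d |
| Only session 1 differs | d − 0.75d = 0.25d | 0.25d − 2.5(0.3d) = −0.50d |

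The same values apply against any single ECIG condition when sequences are equally filled.

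**The case against.** The case for leaving the plan alone has substance.

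- **The flux test is hardly affected.** The Latin square already protects it, and the gain from a session term is small unless drift approaches a full SD, which nothing in the documents supports. A reader might infer that omitting session biases the flux result. With equally filled sequences it does not.
- **The paragraph is permissive.** It says in general and may, and a suitable mixed model is allowed. A reader might infer that the plan rules out the right analysis. It does not; it fails to commit to one. The outright mismatch is confined to the between-group wording.
- **Own brand last is a disclosed design choice.** Neither directional hypothesis rests on it. The first concerns the flux gradient. The second concerns substitution, measured by CP-PRT and the cross-product drug purchase task (CP-DPT), and neither task is run in session 5. This stands. The comparison is nevertheless announced twice as planned, so a caveat is due.
- **A richer model can cost more than it saves.** An unstructured covariance with a session term gives about 0.82, no better than leaving session out at d = 0.5 (0.819) and worse at 0.25 (0.844). This stands too, so the sphericity adjustment already planned is the better companion to the session term.

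**Conclusion.** The concern holds as a mismatch of wording and an unstated model. The default ANOVA and the covariate step refer to groups that this study does not define, and session order is absent from every stated model.

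For flux the consequence is modest: a power loss of about 0.01 to 0.04 for assumed drifts up to 0.5 SD, and a small bias only if replacements leave the sequences unequal. For own brand against ECIG, on the measures taken in session 5 (the single-product drug purchase and progressive ratio tasks, subjective and physiological measures), order and product are aliased. Trend adjustment can remove, reverse or enlarge the bias, and sessions 1-4 cannot show which.

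A reader might also infer that N=32 is an error or that the study is too small. Neither follows: 32 reproduces at five levels, and the planned 40 exceeds the 36 that the four-level flux test needs, with power 0.85 under sphericity.

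These results assume normal outcomes, additive session effects without carryover, and the plan's f and r. The drift sizes, sequence counts and Latin squares are assumptions made for illustration.

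**What to change.** In the Data analysis paragraph:

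1. For the four ECIG sessions, state a within-subject model with condition and session number (1-4) as fixed effects and participant as the blocking or random effect. Keep the planned sphericity adjustment, for example Greenhouse-Geisser. Include the completed sessions of participants who do not finish.
2. Remove the between-group wording and the covariate step, or name the factor they refer to.
3. Report own brand against ECIG separately, as a fixed-order, unblinded comparison with the session 1-4 trend beside it. Give any trend-adjusted estimate only as a sensitivity analysis, with the extrapolation to session 5 stated.

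The cost is a few sentences, 3 error degrees of freedom (117 to 114) and a more cautious own-brand conclusion. With no drift, the session term leaves power at 0.852. N, schedule and procedures stay as they are.

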Cover sheet for protocol HM20018290/NCT04332926

The stats section is from the grant. Our institution now requires a protocol when submitting to the IRB, it was not required when this study was approved. The final version of the study was approved by the IRB 3/21/2024 and the last consent form approved was 2/27/23.

predicted to be the lowest in the 4 mg/ml/8W condition for both exclusive and dual users and highest in the 24 mg/ml/8W condition (exclusive ECIG users' willingness to work 600 vs. 1100 bar presses; dual ECIG+TCig users 375 vs. 690 bar presses). Results revealed that for within-and between-subjects analyses for the $\text{breakpoint}_{\text{MCP}}$ and $\text{breakpoint}_{\text{PRT}}$, 60 participants were required to achieve power $\geq 80\%$ given $\alpha < 0.05$. We excluded own brand controls to ensure we are powered to detect differences across experimental conditions.

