Bonhomme et al., 2016; Wang et al., 2015), and ECIG flavor is associated with increased rewarding properties (Audrain-McGovern et al., 2016), reduced perceived harshness (Kim et al., 2016), and smoking cessation (e.g., Camenga et al., 2016). For Aim 3 sample size and power, we use estimates from [name] et al. (2017) and a repeated measures design predicting outcomes used in Aim 1. For our analyses, we predict the $\text{breakpoint}_{\text{MCP}}$ in the preferred ECIG flavor condition to be more than twice that for the no flavor condition for dual ECIG+TCig users (\$1.30 vs. \$0.52), but exclusive ECIG users will have a breakpoint for the preferred ECIG flavor condition that is more than twice that for dual users (\$3.05). Similarly, elasticity is predicted to be the lowest for the preferred ECIG flavor condition for exclusive ECIG users (elasticity=0.02) and dual users (elasticity=0.05), while elasticity will be highest for no flavor ECIGs (~0.10; supported by [name] et al., 2017). Data from Audrain-McGovern et al. (2016) indicate exclusive ECIG and dual ECIG+TCig users will work 4x harder for their preferred flavor vs. no flavor ECIGs (600 vs. 130 presses), with exclusive ECIG users willing to work more for reinforcers in each condition. For $\text{breakpoint}_{\text{MCP}}$, $\text{breakpoint}_{\text{PRT}}$ and elasticity, using estimates for differences between ECIG liquid flavor condition, within-subjects and between-subjects analyses require 60 participants to achieve power $\geq 80\%$ given $\alpha < 0.05$. In Study 3, 60 exclusive ECIG and 60 dual ECIG+TCig users will attend the lab for 5 sessions. In the first four randomly ordered sessions, they will use an ECIG set at a power setting and liquid with a nicotine concentration informed by the results of Project 2's Study 1 varying only in flavor (preferred flavor, dessert flavor, fruit flavor, and unflavored liquid). Session 5 for all participants will be either an own brand ECIG or own brand tobacco cigarette (ECIG+TCig only) control (see Fig 2). Products for own brand ECIG and tobacco cigarette conditions and session procedures will be as in Study 1. We hypothesize that abuse liability indices will vary by flavor more for exclusive vs. dual users (preferred > dessert/fruit > none). This pattern highlights how ECIG abuse liability is affected by flavor availability.

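### Tukey's HSD is allowed for the pairwise follow-up, but its usual pooled error is valid only under sphericity; contrast-specific errors with Holm would be a cheap improvement

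*Combined protocol and SAP*

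**What the plan says.** The analysis text is in Study Procedures, item 6, under Data analysis. One sentence covers both sphericity and follow-up testing: "Adjustments for sphericity violations and post-hoc testing using Tukey's HSD or planned contrasts with Bonferroni corrections will be used". It does not say which post-hoc method applies when, what error term the pairwise tests use, or whether the sphericity adjustment reaches them. The sentence before it leaves the model open: "Statistical analyses may utilize regression, ANOVA, or mixed linear models".

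The sample size justification (Study Population, item 3) is framed "in a repeated measures ANOVA with nicotine flux as within-subjects factors (N=32; GPower", with effect size f = 0.20 and correlation 0.5. The conditions are "no flux, low flux, cigarette-like flux, high flux, and an own brand cigarette control (always session 5"). Accrual continues until 40 participants complete the study.

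No SD, covariance matrix or sphericity epsilon is given for any outcome. The only hints about spread are indirect and come from sibling studies in the grant text. One predicts breakpoints across nicotine and power conditions ("willingness to work 600 vs. 1100 bar presses; dual ECIG+TCig users 375 vs. 690 bar presses"). The Aim 3 flavor study predicts "600 vs. 130 presses" for preferred against no flavor.

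**The concern.** The omnibus F and the pairwise tests need sphericity in different ways. A Greenhouse-Geisser type correction shrinks the degrees of freedom of the F test. Tukey's HSD on a within-subject factor divides every pairwise difference by a standard error built from the same condition-by-subject mean square. If the variances of the pairwise differences are unequal, that standard error is too large for some pairs and too small for others. The first kind lose power and the second kind are rejected too often. Familywise error can stay close to 0.05 because the two faults offset each other.

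Unequal variances are plausible here. The PRT requirement grows by 30% per puff, so breakpoint lies on a geometric scale, and responding in the 0 mg/ml condition could sit near the floor. The study asks how abuse liability changes with flux. Any statement about which flux levels differ from one another would rest on these pairwise tests.

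**Working it through.** **Plan's own figure.** For a within-subject ANOVA, lambda = f² × N × m × epsilon / (1 − r), with df1 = (m − 1) × epsilon and df2 = (N − 1)(m − 1) × epsilon. With m = 5 and epsilon = 1, N = 32 gives lambda = 0.04 × 32 × 5 / 0.5 = 12.8, df 4 and 124, and power 0.814; N = 31 gives 0.799. So the stated N = 32 reproduces, and it corresponds to exact sphericity. With 40 completers the omnibus power is 0.90 at epsilon 1, 0.83 at 0.75 and 0.76 at 0.6.

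**Inputs for the pairwise check.** From the documents: N = 40, r = 0.5, four ECIG conditions (six pairs). Assumed: SDs rise from 1 to R, spaced evenly or geometrically, with a common correlation. R is bracketed by the grant's predicted mean ratios, 1100/600 = 1.83 (690/375 = 1.84 for dual users) and 600/130 = 4.6, on the further assumption that SD is proportional to the mean.

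**Formulas.**
- True variance of a paired difference: v = s_a² + s_b² − 2 r s_a s_b.
- Pooled version: 2MS = 2 × (mean variance − mean covariance), which is the average of the six v.
- Tukey critical value in t units: q(0.05; 4, 117)/√2 = 3.686/√2 = 2.606, where 117 = 39 × 3. Nominal rate per pair: 0.0103.
- Paired Bonferroni critical value: t with 39 df at 0.05/6 two-sided = 2.780. The noncentrality for 80% power is 3.644.
- With k = √(2MS/v), Tukey power for the lowest pair is approximately Φ(3.644 − 2.606 k). The null rejection rate for the top pair is approximately 2Φ(−2.606 k), using that pair's own k.

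**Worked case, R = 1.83, even spacing (1, 1.28, 1.55, 1.83).** Lowest pair: v = 1 + 1.638 − 1.280 = 1.358. Top pair: v = 2.4025 + 3.3489 − 2.8365 = 2.915. Pooled 2MS = 2.224. For the lowest pair k = √(2.224/1.358) = 1.280, so the Tukey threshold is 3.335 true standard errors and power is Φ(0.309) = 62%. For the top pair k = √(2.224/2.915) = 0.874, so null rejection is 2Φ(−2.277) = 2.3%.

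**Results**

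| R | Spacing | k, lowest pair | Power, formula | Power, simulated | k, top pair | Null top pair, formula | Null top pair, simulated |
|---|---|---|---|---|---|---|---|
| 1 | equal | 1.00 | 85% | 85% | 1.00 | 0.9% | 1.0% |
| 1.83 | even | 1.28 | 62% | 61% | 0.87 | 2.3% | 2.5% |
| 1.83 | geometric | 1.30 | 60% | 60% | 0.87 | 2.4% | 2.5% |
| 3 | even | 1.58 | 32% | 33% | 0.84 | 2.8% | 3.0% |
| 3 | geometric | 1.72 | 20% | 22% | 0.83 | 3.1% | 3.4% |
| 4.6 | even | 1.82 | 14% | 15% | 0.84 | 2.9% | 3.0% |
| 4.6 | geometric | 2.25 | 1% | 2% | 0.81 | 3.4% | 3.7% |

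The formula treats the pooled mean square as known; the simulations (20,000 or more trials per case) do not. Across all simulation runs the ranges are 60-64% at R = 1.83, 22-33% at 3 and 2-16% at 4.6. Null top-pair rejection is about 2-4% and Tukey familywise error 0.053-0.072. Paired Bonferroni holds 80% by construction, with familywise error of about 0.04.

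**Sensitivity.**
- Applying a Greenhouse-Geisser df correction to Tukey changes power only from 0.325 to 0.320 at R = 3 (even spacing).
- Correlations of 0.3 and 0.7 give 34% and 30% at R = 3.
- With own brand as a fifth condition, its SD equal to that of 30 mg/ml, power is 54% at 1.83, 20% at 3 and 6% at 4.6.
- Bonferroni with the pooled error has the same fault: 23% power at SDs 1, 1.5, 2, 3.

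**The case against.** The plan does not say that it expects nonsphericity, and it never states a pooled error. A reader might infer both, but the text only provides for violations, and the pooled error is the textbook form of Tukey's HSD rather than the plan's wording. The same paragraph also permits Bonferroni planned contrasts and mixed models. All of this stands. It does not remove the point, because Tukey remains an open choice and the Bonferroni option helps only if each contrast has its own error term.

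The SD ratios are assumed. The grant's predictions concern ECIG users in studies of other manipulations, and going from a ratio of means to a ratio of SDs is a second assumption. That also stands, and it is why the result is a range. A further weakness is that if SD strictly follows the mean, two conditions with equal means also have equal SDs. In that premise-consistent case the null top pair is rejected at 2.3-3.1%: still above the nominal 1%, and still modest.

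A tempting stronger reading is that low-flux contrasts lose most of their power while high-flux ones are over-called. The documents do not support this as a general statement. It needs SD to rise with flux, and a loss of more than half needs a ratio of about 2.5 or more. Price sensitivity is hypothesised to move against flux, so the pattern may reverse for elasticity. CP-PRT breakpoint is bounded at 10 trials, so proportional scaling is doubtful there. With equal SDs and serial correlation the distortion falls on adjacent against distant pairs instead. The hypotheses are directional and do not name adjacent steps.

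Finally, the data preparation is described only by reference to other reports. If it includes a log transform, proportional SDs would be stabilised and Tukey would be slightly the better choice.

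**Conclusion.** The point holds as a cheap improvement. The plan makes provision for nonsphericity and still permits a follow-up method whose standard form assumes sphericity, and correcting the omnibus test does not change that. The method costs nothing if the SDs are equal (84-85% power against 80% for paired Bonferroni). It costs 16 to 20 points at an SD ratio of 1.83, which is about a quarter of the power at most, and far more at ratios of 3 and above. The inflation of error is real but small: each null pair stays below 5%, and familywise error is about 0.05-0.07. These sizes rest on assumed SDs, a common correlation, multivariate normal data and 40 completers. The documents do not establish any particular SD ratio or which flux steps would be affected.

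**What to change.** Delete the Tukey option and name the error term. For example: for each outcome, the four ECIG conditions will be compared by six pairwise contrasts, each tested against the standard error of its own within-participant differences (or as contrasts from a linear mixed model with unstructured covariance across conditions), with Holm adjustment over the six. Comparisons with own brand should use the same kind of error term, and the plan should say which multiplicity family they belong to.

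The cost is one sentence of analysis text, with no change to procedures or data collection. If sphericity holds exactly, Holm-adjusted paired contrasts have about 83% power against Tukey's 84-85%, a loss of about 2 points; with plain Bonferroni the loss is about 5 points. If sphericity fails, the change preserves the power of the low-variance pairs and keeps the error of the high-variance pairs under control.
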